#### **Purpose**

This pilot study will examine the feasibility, acceptability, and preliminary impact of using NicoBloc compared to nicotine lozenges. Forty (n=40) participants will be randomized to one of two interventions 1) NicoBloc or 2) nicotine lozenge. All participants will complete approximately 60 minutes of baseline assessment to determine smoking history and characteristics prior to randomization, including previous experience with NRT.

### **Analysis strategy**

Feasibility and acceptability will be measured through high study retention (70%) and recruitment (recruitment of all participants within 24 months) in our groups. Additional items of acceptability include high scores on treatment satisfaction and credibility/expectancies that are equal or higher to the NicoBloc group. Medication adherence is a third primary outcome with expected differences between our groups. Adherence is notoriously difficult to determine. Self-reported adherence is not always reliable, particularly during treatment studies where there is a demand characteristic to report the desired targeted behavior (e.g., adherence to medication). The behavioral methods described under the assessment section represent the best available self-report tools for determining NRT adherence (e.g., Timeline Follow Back (TLFB) report, returning used products and packaging). Adherence will be defined by self-report using the TLFB and verified through returned patches and packaging. Good adherence is defined by taking greater than 80% of doses of medication at each time point.

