#### **Procedure**

A urine drug screen and pregnancy test for females will be obtained during the screen visit. If positive, participants will be screen failures and will not be enrolled in the study. Specimens will not be

distributed or stored. They will be labeled with a unique study identifier. There will be no clinical data associated with the specimens. They are used only to establish eligibility for the study.

After eligibility determination and consent to participate, the baseline assessments will be administered. This assessment is expected to take about 60 minutes and will provide basic smoking history, smoking behavior, and proposed mediators and moderators such as treatment interest, expectancies for NRT and NicoBloc, previous use of NRT, craving, withdrawal, and side effects associated with NRT use (see Table 1 description) and will be repeated during the study period (see Table 2 for assessment schedule). At each visit the participant will have a carbon monoxide test (CO) which will determine how much CO is in the lungs. At the baseline visit, participants will be asked to prolong smoking as long as they can on the days of the study sessions. Female participants will be screened monthly for pregnancy.

Participants will be randomized to either NicoBloc or Nicotine Lozenge and will undergo the following interventions. Interventionists will be undergraduate level research assistants (RAs) with degrees in psychology or a related field. They will be trained to follow the manual and deliver both behavioral interventions by the PI, although they will not have extensive tobacco training. All sessions will be audiotaped and 20% will be coded for treatment fidelity to ensure no contamination between behavioral interventions.

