A Pilot Trial Comparing NicoBloc to Nicotine Lozenges: Initial Acceptability and Feasibility Trial 2/2/2022 NTC:300001370

Data Analytic Approach

Participant screening, baseline eligibility, baseline attendance, study eligibility, and retention rates throughout the study were calculated overall and per time point. Retention rates between groups at each time point and other dichotomized variables such as adherence were assessed using Chi-Square analyses. Participant demographics and baseline smoking characteristics were assessed, and group differences examined using measures of effect size (Cramer's *V* and Cohen's *d*). Group differences over time were analyzed using generalized estimating equations (GEEs) with all available data (i.e., Intent-To-Treat analyses). GEE results were followed-up with pairwise comparisons when applicable. Measures administered pre- and post-session (QSU and MNWS) were calculated as a change score and included as such in GEE analyses. Pre-session scores were subtracted from post session scores such that negative scores reflect decreases in withdrawal symptoms or smoking urges throughout the session. For measures administered at two or less time points, *t*-tests were used to examine group differences.

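### Acceptability is judged partly by scores that are equal or higher between arms, but the SAP offers only tests of difference, with no interval or tolerance that could support 'equal'

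*Protocol*

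**What the plan says.** The protocol's Analysis strategy measures feasibility and acceptability through retention (70%) and recruitment within 24 months. It then adds acceptability items: "high scores on treatment satisfaction and credibility/expectancies that are equal or higher to the NicoBloc group". It gives no cut-off for 'high', no tolerance for 'equal' and no decision rule. Read literally, NicoBloc, the product under study, is the reference and the other arm has to match or exceed it.

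The SAP's Data Analytic Approach does not mention satisfaction or credibility/expectancy. Two general rules could cover them:

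- Repeated measures: "Group differences over time were analyzed using generalized estimating equations (GEEs) with all available data", followed by pairwise comparisons where applicable.
- Measures taken once or twice: "For measures administered at two or less time points", t-"tests were used to examine group differences".

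Effect sizes do appear in the SAP, but for another purpose: "Participant demographics and baseline smoking characteristics were assessed, and group differences examined using measures of effect size". Neither document contains an equivalence or non-inferiority analysis, a margin or a confidence-interval rule.

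**The concern.** The protocol asks for a statement of similarity or better, and the SAP plans analyses that can only give evidence of a difference. Nothing links the two, so whoever writes the results must decide, possibly after seeing the data, what counts as 'equal'. The easiest default is to read a non-significant test as equality. In a small trial that default favours a pass, and a pass becomes easier as participants are lost.

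Acceptability is one of the pilot's stated purposes, and the result would naturally inform whether the product is taken further. A conclusion of equal acceptability that rests mainly on a small sample would mislead at that point.

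**Working it through.** The documents give no power, effect-size or sample-size calculation, so there is no planned figure to reproduce. The check asks what a non-significant test could tell us at this sample size.

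**Inputs**

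- Total size (protocol, Purpose): "Forty (n=40) participants will be randomized to one of two interventions".
- Allocation: the Procedure says only "Participants will be randomized to either NicoBloc or Nicotine Lozenge". I assume 1:1, so n = 20 per arm.
- Evaluable number if retention just meets the 70% target: 0.70 × 20 = 14 per arm.
- Significance level: not stated; two-sided 5% assumed.
- SD of the scores: not stated, so differences are in SD units (SD = 1).
- Analysis: one t-test at a single time point. This is an assumption, because the assessment schedule table that the Procedure cites is not in the text available for this review.

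**Step 1. Precision.** The 95% CI half-width is t(0.975, 2n−2) × √(2/n).

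- n = 20: 2.024 × 0.316 = 0.64 SD.
- n = 14: 2.056 × 0.378 = 0.78 SD.

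A non-significant result is therefore compatible with differences well beyond half an SD.

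**Step 2. Non-significance read as equality (an inferred reading).** For an arm truly worse by d, the test statistic is noncentral t with 2n−2 degrees of freedom and noncentrality d × √(n/2). The probability that the arm is not found significantly worse is the noncentral t distribution function at t(0.975, 2n−2).

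| True shortfall | n per arm | Noncentrality | Probability of passing |
|---|---|---|---|
| 0.5 SD | 20 | 0.5 × 3.162 = 1.581 | 66% |
| 0.5 SD | 14 | 0.5 × 2.646 = 1.323 | 75% |
| 0.8 SD | 20 | 0.8 × 3.162 = 2.530 | 31% |
| 0.8 SD | 14 | 0.8 × 2.646 = 2.117 | 47% |

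At both shortfalls, losing participants raises the chance of passing. The figures are the same whichever arm is the reference.

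**Step 3. Observed means compared directly (also inferred).** The probability that the observed mean is at least as high is Φ(−d × √(n/2)). This is 50% at d = 0. At d = 0.5 it is Φ(−1.581) = 6% with 20 per arm and Φ(−1.323) = 9% with 14.

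**Step 4. An interval against a tolerance.** Take 0.5 SD as an illustrative tolerance and a two-sided 90% CI, and conclude 'equal or higher' only if the lower limit lies above −0.5 SD. An arm truly 0.5 SD worse then passes 5% of the time. A truly equal arm is confirmed with probability 1 − F(t(0.95, 2n−2)), where F is the noncentral t distribution function with noncentrality 0.5 × √(n/2):

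- n = 20: critical value 1.686, noncentrality 1.581, confirmed 46%.
- n = 14: critical value 1.706, noncentrality 1.323, confirmed 36%.

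A truly equal arm would be called lower 5% of the time (upper limit below zero). That leaves about 100 − 46 − 5 = 49% inconclusive with 20 per arm and 100 − 36 − 5 = 59% with 14.

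**The case against.** **The rule is inferred.** Neither document says that p > 0.05 means equal, and a pilot may intend only a descriptive benchmark: scores that are high and about as good as the comparator's. This stands in part. A reader might infer that the trial will declare equality from non-significance, but the documents do not say so. What remains is that they offer no other basis for 'equal', and the only between-arm analyses that could apply to these scores are tests of difference.

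**It is not the only acceptability evidence.** A reader might take this comparison to decide acceptability alone. It does not: the protocol also ties feasibility and acceptability to retention, which the SAP compares between arms by chi-square at each time point.

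**A clearly worse arm would not always pass.** Correct. At 0.8 SD worse, passing is the minority outcome at both sample sizes; only the 0.5 SD case passes more often than not.

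**The remedy does not confirm equality more often.** Also correct. A truly equal arm is confirmed 46% of the time with 20 per arm, against 50% when observed means are simply compared, and both approaches mostly reject an arm 0.5 SD worse (5% and 6% pass). So the figures do not show that the interval rule is the sharper classifier. Its gain is that it shows the uncertainty and separates inconclusive from lower, where a bare comparison of means must return a pass or a fail.

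**Scores may be repeated.** If they are collected at more than two time points, GEE on all available data applies and the percentages in Step 2 need not hold. The mismatch of aim and method remains, because GEE as planned also examines differences.

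**Conclusion.** The concern holds. The planned tests of difference cannot support a conclusion that one arm's satisfaction or credibility/expectancy is equal to or higher than the other's, unless it is significantly higher, because no interval or tolerance is specified. If non-significance were used as the criterion, an arm 0.5 SD worse would pass 66% (20 per arm) to 75% (14 per arm) of the time, and one 0.8 SD worse 31% to 47%.

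The percentages rest on 1:1 allocation, a single-time-point t-test, a two-sided 5% level and shortfalls expressed in SD units. None of these is given in the documents. The mismatch itself depends on none of them.

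A reader might go further and infer that the pilot needs a powered non-inferiority comparison. The documents do not support that: the stated aims are feasibility, acceptability and preliminary impact. The point is an inexpensive correction to how one acceptability criterion is analysed and worded.

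**What to change.** In the protocol's Analysis strategy and in the SAP:

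1. State which arm is compared with which, for example NicoBloc minus lozenge, so that the sign of the difference is fixed.
2. Keep the requirement for high scores and give it a cut-off on each instrument, so that two poorly rated products cannot satisfy the criterion by resembling each other.
3. Report each score's arm difference with a confidence interval, from the t-test or the GEE as the schedule requires, and state that p > 0.05 is not read as equality.
4. Set a tolerance in scale points for each instrument. Conclude 'lower' if the upper limit is below zero; otherwise conclude 'equal or higher' if the lower limit lies above minus the tolerance; otherwise report 'inconclusive'. Giving 'lower' precedence settles the rare case in which both conditions are met.
5. The SAP is dated 2/2/2022 and written in the past tense. If the data have already been analysed, label the tolerance as post hoc.

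This costs wording and a few lines of output on the same data, with no extra participants. The tolerance needs a justification that the documents do not supply; the 0.5 SD used above is only an illustration. The real downside is a less favourable statement: with 40 participants inconclusive is a likely result, and the acceptability finding should be presented as preliminary.

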## Background

Summarize in 2-3 paragraphs past experimental and/or clinical findings leading to the design of this protocol. Include any relevant past or current research by the PI. For drug and device studies, summarize the previous results (i.e., Phase I/II or III studies).

Smoking remains the leading cause of preventable death in the U.S. with approximately 18% of the population continuing to smoke. However, smoking is concentrated in disadvantaged populations where the prevalence of smoking may be as high as 70-80 %. Participants will receive a sampling experience (use of nicotine lozenges or NicoBloc during sessions) with counseling focused around their experience of using these interventions, including side effects and smoking cessation expectancies.

NicoBloc is a pink occlusion fluid supplied in 15 ml bottles. Three drops applied to a cigarette filter will trap up to 99% of tar and nicotine in the filter (depending upon cigarette brand). The ingredients of NicoBloc are: Corn Syrup (86.83%), Water (12.76%), Citric Acid (E330) – acidity regulator (0.30%), Sodium Benzoate (E211) – food preservative (0.05%), Potassium Sorbate (E202) – food preservative (0.05%), Allura Red 40 (E129) – red food colouring (0.01%). These ingredients are classified as FDA approved food grade ingredients.

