NicoBloc: NicoBloc participants will be provided with NicoBloc to use in each 30-minute session and will test smoking their conventional cigarette with NicoBloc. In session, they will discuss their experience of smoking their cigarette with NicoBloc at each of the sessions. For Session 1, participants will use one drop of NicoBloc (which will block 33% of tar and nicotine) on their conventional cigarette and then will smoke this cigarette in session. Following smoking, they will discuss the effects of the NicoBloc on their withdrawal, cravings, and overall enjoyment of their cigarette. To bolster their in vivo NicoBloc experience, participants will be provided with NicoBloc to use between sessions to acclimate to the NicoBloc and to make practice quit attempts (PQAs). Sessions 2 and 3 are similar to Session 1 except they will use more NicoBloc product during the session and will be instructed to use the product between sessions. For example, in Session 2, they will use 2 drops on their cigarettes (which blocks about 66% of tar and nicotine) and then smoke. Similarly, in Session 3 they will use 3 drops of NicoBloc which is equivalent to blocking 99% of the tar and nicotine exposure from a cigarette and then smoke. At Session 4 they will discuss their experiences using NicoBloc and will set a quit date prior to their 8 week visit. Participants will return at 8 and 12 weeks (EOT) with a final one month follow-up at Week 16.

Nicotine Lozenge: Participants who receive nicotine lozenge (mini lozenge) will be given either a 2 or 4 mg lozenge to use in session, depending on how soon they smoke after waking. If a participant smokes within 30 minutes of waking, they start with the 4 mg lozenge; more than 30 minutes, they start with the 2 mg lozenge. Similar to NicoBloc, they will use the lozenge in session and will discuss the effects of using the lozenge in session. They will do this for all four Sessions and will be given lozenges between sessions to make PQAs. They will be asked to set a quit date during Session 4 similar to the NicoBloc participants.

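### One 80%-of-doses adherence rule covers both arms, but a NicoBloc dose needs a smoked cigarette, so after the quit date, chiefly at Week 12, NicoBloc adherence depends partly on quitting

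*Protocol*

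**What the plan says.** The protocol's Analysis strategy states: "Medication adherence is a third primary outcome with expected differences between our groups". It gives one cut-off, "Good adherence is defined by taking greater than 80% of doses of medication at each time point", and one method of measurement: "Adherence will be defined by self-report using the TLFB and verified through returned patches and packaging". (Neither arm uses patches.) The Procedure section uses the word medication for both NicoBloc and lozenge, so the rule applies to both.

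The Background describes NicoBloc as a filter treatment: "Three drops applied to a cigarette filter will trap up to 99% of tar and nicotine in the filter". The Procedure has participants put one, two and then three drops on a cigarette and smoke it. No use apart from a cigarette is described. The lozenge is 2 or 4 mg, and taking it does not require smoking.

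At Session 4, NicoBloc participants "will set a quit date prior to their 8 week visit". For the lozenge arm: "They will be asked to set a quit date during Session 4 similar to the NicoBloc participants". Both arms then receive product for eight more weeks to support a lasting quit attempt, with visits at Weeks 8 and 12.

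The SAP (Data Analytic Approach) lists adherence among the dichotomized variables compared by Chi-Square. Neither document, as supplied, gives a dose denominator for either product or says how to score a NicoBloc participant who has stopped smoking.

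**The concern.** The trial asks participants to quit, and a NicoBloc participant who does so has no cigarette on which to take a dose. A lozenge participant who quits can still take every dose. The same rule therefore measures different things in the two arms once quitting starts.

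Each way of scoring a NicoBloc quitter has a cost. Scoring them non-adherent marks the arm down for succeeding. Leaving them out compares a group formed after randomization. Scoring them adherent credits quitting as product use. A low NicoBloc rate could then mean that people rejected the product or that they no longer needed it, and a reader could not tell which. That matters because adherence is a named primary outcome on which the arms are expected to differ. Practice quit attempts between Sessions 1 and 4 raise the same issue on a smaller scale.

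**Working it through.** The plan gives no adherence rate, quit rate, alpha or power, so there is no figure of its own to reproduce. What follows is a sensitivity check.

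**Inputs.** From the documents: 40 participants in two arms, the 80% cut-off, a 70% retention target, and Chi-Square. Assumed: 20 per arm (the allocation ratio is not stated); two-sided 0.05; true adherence A = 60% in both arms among those with doses due; and a NicoBloc fraction q with no cigarettes in the scored interval, unrelated to adherence.

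**Expected NicoBloc rate.**
- Quitters non-adherent: A(1 − q)
- Quitters excluded: A
- Quitters adherent: A(1 − q) + q

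The gap between the first and third is exactly q, whatever A is.

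| q | Non-adherent | Excluded | Adherent |
|---|---|---|---|
| 10% | 54% | 60% | 64% |
| 20% | 48% | 60% | 68% |
| 30% | 42% | 60% | 72% |

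Against a lozenge rate of 60%, q = 20% gives differences of −12, 0 and +8 points when there is no true difference.

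**If lozenge quitters also cut down.** Let 20% of the lozenge arm quit, and let s be the share of the otherwise adherent quitters who stay above 80%. The lozenge rate is A(1 − q) + A·s·q.
- s = 0.5: 0.48 + 0.06 = 54%, with differences −6, +6 and +14.
- s = 0: 48%, with differences 0, +12 and +20.

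The differences shift, but the 20-point spread across scorings stays.

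**Which visit.** Counted per cigarette, 0/0 needs an entire interval without smoking. Someone whose quit date falls between Session 4 and Week 8 will usually have smoked for part of that interval and can be scored on those cigarettes, so the undefined case arises mainly at Week 12. Against a fixed daily count, six smoke-free days in 28 give 22/28 = 78.6%, below the cut-off, so Week 8 is affected as well.

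**Effect on the test.** Exact enumeration of two independent binomials, p < 0.05, lozenge at 60%:

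| Setting | No quitters | q = 20%, non-adherent | q = 20%, adherent |
|---|---|---|---|
| 20 per arm, uncorrected | 4.8% | 10.6% | 8.4% |
| 20 per arm, continuity-corrected | 1.9% | 5.4% | 3.7% |
| 14 per arm (70% of 20), uncorrected | 4.6% | 8.4% | 7.0% |

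For 20 per arm uncorrected, q = 10% and 30% give 6.1% and 18.6% (non-adherent) or 5.8% and 13.0% (adherent). Excluding quitters leaves the rate at about 5%. With lozenge at 54% and q = 20%, the rates are 5.7% (non-adherent) and 14.5% (adherent).

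**Precision.** The 95% half-width for a difference is 1.96 × √(2 × 0.6 × 0.4 / 20) = 0.304, about 30 points.

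**The case against.** The strongest reply is that the definitions may exist elsewhere. The Analysis strategy refers to an assessment section, and the Procedure refers to Tables 1 and 2; none of these is in the supplied text. If they state denominators, only the scoring of abstinent NicoBloc participants may remain open. That stands as a limit on the point. A reader might infer that the trial never defined a dose, and the documents do not support that.

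A reader might also infer that Weeks 8 and 12 are equally affected, or that the SAP plans a separate adherence test at each. Neither is established. Per cigarette is the more natural way to count NicoBloc doses, and under it Week 8 is usually scoreable. The SAP sentence attaches the per-visit wording to retention, and the protocol's cut-off could also be read as one status requiring adherence at every visit.

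It is fair, too, that every rate above is assumed, that the inflation depends on the version of the test, and that a 40-person pilot with an interval of about ±30 points, and no target for the proportion adherent, will not turn on this test. Lozenge use may also fall after quitting.

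None of this removes the asymmetry. A lozenge quitter can take doses and a NicoBloc quitter cannot, and every reading of a dose leaves that quitter failing, undefined or passing by convention.

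**Conclusion.** The point holds for the supplied text as a flaw in the stated rule, and correcting it is a cheap improvement. After the Session 4 quit date, NicoBloc adherence is tied to quitting, chiefly at Week 12, and at Week 8 too under a fixed dose count. The NicoBloc rate can move by up to the NicoBloc quit rate, which is 20 points between the extreme scorings at an assumed 20% quitting.

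A reader might infer a bias against NicoBloc, or a seriously invalid test. The documents support neither: the direction depends on a scoring rule that they do not give, and the effect on the Chi-Square is modest under the assumptions shown (20 or 14 per arm, 60% adherence, quitting unrelated to adherence). What is lost is mainly the meaning of the adherence comparison.

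**What to change.** Define each denominator. For NicoBloc: cigarettes treated at the assigned drop count divided by cigarettes smoked in the interval, so that someone who quits partway is scored on what they did smoke. For lozenge: lozenges taken divided by a stated expected number. If the assessment section already contains these, point to it and add only the rule for abstinent participants.

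At Weeks 8 and 12, make a three-category table the main presentation in both arms: adherent, non-adherent and abstinent. Define abstinent identically in each arm as no cigarettes on the TLFB in the interval. CO is already taken ("At each visit the participant will have a carbon monoxide test (CO) which will determine how much CO is in the lungs"), but use it as a supporting check only, because one visit reading cannot confirm a whole interval.

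For the Chi-Square, name one scoring of abstinent NicoBloc participants as primary and show the other two as sensitivity analyses. Three versions without a primary would leave the ambiguity in place.

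The cost is two definitions, one table and two extra runs of one test, with no added participants or visits. The comparison becomes less simple, and the TLFB must record both cigarettes smoked and cigarettes treated, which the supplied text does not confirm. The SAP is written in the past tense, so if treated cigarettes were not recorded, report the table as far as the TLFB allows.
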